Entry into the study will depend on the patient's blood results confirming the need for NAC. A total of 24 patients will be assigned into one of 3 dosing cohorts of 8 patients (N=6 for PP100-01 and NAC; N=2 for NAC alone).

The study will primarily evaluate safety and tolerability for treatment with PP100-01 in combination with NAC as compared to NAC alone.

Baseline Assessments:

Blood tests, vital signs, physical examination and an ECG will be completed as part of the baseline assessments.

NAC will be given to all patients arriving to the hospital according to the standard guidelines when paracetamol/acetaminophen overdose is suspected. All patients that arrive to the hospital within 24 hr of POD and require NAC treatment will be asked if they will participate in the study once their blood results are available. The following investigations will be performed as part of clinical care on arrival to hospital or 4hrs after overdose (whichever is the longer time):

- Paracetamol level in serum/plasma
- Urea and electrolytes and creatinine
- Liver function tests (LFTs) ALT, Bilirubin and ALP
- Clotting screen: INR and Prothrombin time (PT)

Treatment Phase:

Patients that have signed the informed consent will be treated with NAC and randomised to NAC alone (N=2 per dosing cohort) or PP100-01 and NAC (N=6 per dosing cohort)

- Group A: PP100-01 (2 µmol/kg calmangafodipir) after the "loading" dose of NAC
- Group B: PP100-01 (5 µmol/kg calmangafodipir) after the "loading" dose of NAC
- Group C: PP100-01 (10 µmol/kg calmangafodipir) after the "loading" dose of NAC

PP100-01 treatment is administered intravenously over 5 minutes.

The NAC regime will be continued with the second dose: 200 mg/kg NAC in 1000 ml i.v. over 10hr.

The following procedures should be performed during the treatment phase:

- ALT bilirubin and alkaline phosphatase (ALP)
- Prothrombin time and INR
- Serum creatinine
- Biomarkers: CK18 and microRNA MiR122, GLDH, mitochondrial DNA and others

End of treatment:

At the end of the 12hr NAC regimen the decision to continue NAC is made by:

- the ALT has more than doubled since the admission measurement, OR
- the ALT is two times the upper limit of normal or more, OR
- the INR is greater than 1.3 (in the absence of another cause, e.g. warfarin)
- paracetamol/acetaminophen concentration greater than 20 mg/mL

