7.1.7 Treatment Phase

Treatment will start with the first NAC bag of 100 mg/kg in 200 ml ("loading dose") at time point '0'. Immediately prior to PP100-01 a study specific blood sample will be collected (time 2hr).

PP100-01 treatment is administered intravenously as a bolus infusion over 5 minutes at the dose specified by the dosing cohort:

- Group A: PP100-01 (2 µmol/kg calmangafodipir) after the "loading" dose of NAC
- Group B: PP100-01 (5 µmol/kg calmangafodipir) after the "loading" dose of NAC
- Group C: PP100-01 (10 µmol/kg calmangafodipir) after the "loading" dose of NAC

All necessary precautions will be taken during administration of the study drug. The patient will be monitored with vital signs (Section 7.1.3). Observation and medical treatment for anaphylactic shock will, as a standard be requisite.

The 12hr NAC regime will be continued with the second dose: 200 mg/kg NAC in 1000 ml i.v. over 10 hr. As per routine clinical practice, there will be one blood sample taken 2 hrs before the end of the second NAC bag (the 10hr time-point) and a second blood sample taken 10h later (the 20hr time-point).

The following procedures should be performed during the treatment phase at time-points: baseline, 2hr, 10hr and 20hr (see study schedule, section 7.2 (Table 1)):

• ALT, bilirubin and alkaline phosphatase (ALP)

- Prothrombin time and INR
- Serum creatinine
- Biomarkers: CK18 and microRNA MiR122, GLDH, mitochondrial DNA and others
- PP100-01 level will be assessed at 2hr, 10hr and 20hr

Any rescue medication given will be recorded in the Case Report Form by routine clinical staff.

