7.1.9 Adverse events

Adverse events/ adverse reactions will be assessed at baseline, 2hr, 2.5hr 10hr, 20hr and 22hr and as part of follow up (section 7.1.10). A full physical exam will be carried out if AEs/SAEs are identified that require a more thorough exam to be performed and this will be recorded on the CRF.

Episodes and incidence of vomiting and retching will be recorded objectively by nursing staff on the AE log and reported as an SAE if classified as serious.

Adverse events will be recorded and reported as detailed in Section 11.

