7.1.11 Assessment timelines

2, 2.5 hour assessments should be performed +/-15mins of the timepoint. PP100-01 treatment should be +/- 10mins of timepoint. 10, 20 hour assessments should be performed +/-30minutes of the timepoint.

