10.3 Detecting AEs and SAEs

All AEs and SAEs must be recorded from the time a participant consents to join the study until hospital discharge.

The Investigator should ask about the occurrence of AEs/SAEs during the infusion and until hospital discharge. Open-ended and non-leading verbal questioning of the participant should be used to enquire about AE/SAE occurrence. If there is any doubt as to whether a clinical observation is an AE, the event should be recorded.

Patient electronic records will be reviewed at 7 days, 30 and 90 days after discharge for AEs and SAEs.

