4.4 Primary Outcome (Safety population)

The number and percentage of patients experiencing an adverse event (AE) will be summarised by treatment group and overall. Further tabulations in the same format will be reported for subsets of AEs according to the following criteria:

- Serious adverse events (SAEs)
- AEs starting after the commencement of NAC treatment and within 7 days of consent
- SAEs starting after the commencement of NAC treatment and within 7 days of consent
- Intensity (mild/moderate/severe)
- Treatment given in response to AE (yes/no)

- Outcome (recovered/improved/unchanged/deterioration/death)
- Relationship to NAC (unrelated/possibly related/probably related/definitely related)
- Relationship to PP100-01 (unrelated/possibly related/probably related/definitely related)
- Action taken with NAC (none/interrupted/stopped entirely)
- Action taken with PP100-01 (none/interrupted/stopped entirely)¹
- Unexpected with, and related to, NAC
- Unexpected with, and related to, PP100-01
- Suspected unexpected serious adverse reaction (SUSAR), subcategorised into SUSAR to NAC; SUSAR to PP100-01; SUSAR to NAC and PP100-01

The number and percentage of patients experiencing an adverse event will also be reported according to MedDRA system organ class (SOC). Results will be presented separately for AEs not classified as serious, for SAEs and for all AEs. Events will be summarised by (a) treatment group and overall, and (b) by treatment received (NAC or PP100-01+NAC) within each dosing cohort.

Primary analysis

The numbers of participants experiencing AEs and SAEs will be reported by treatment group and overall using the proportion and exact 95% confidence interval. AE and SAE proportions will be compared within each dosing cohort between the PP100-01+NAC and the NAC alone patients using a difference in proportions and its exact 95% confidence interval. AE and SAE rates will be compared between each of the PP100-01 2µmol/kg, 5µmol/kg and 10µmol/kg groups and the combined NAC alone group in the same way.

If the limited sample size or a small number of observed events leads to a lack of interpretability of the formal analysis confidence intervals, the analysis of the primary outcome will be restricted to descriptive summaries only.

Missing data

We do not anticipate missing data impacting on the analysis of the routinely recorded adverse event data that form the primary outcome.

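### The AE comparison has no onset limit and no AE table starts at the PP100-01 bolus, so events before the bolus can dilute the any-AE contrast (minor)

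*SAP*

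**What the plan says.** The primary analysis in SAP 4.4 reads: "AE and SAE proportions will be compared within each dosing cohort between the PP100-01+NAC and the NAC alone patients using a difference in proportions". Each dose group is then compared with the pooled NAC-alone patients in the same way. Neither sentence restricts when an event must have started.

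SAP 4.4 does have an onset window, but only among its subsets: "AEs starting after the commencement of NAC treatment and within 7 days of consent", with a matching row for SAEs. These rows are tabulations, not comparisons ("Further tabulations in the same format will be reported for subsets of AEs according to the following criteria"), and they begin at NAC, not at PP100-01.

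The protocol sets the timing:
- Recording starts at consent (Protocol 10.3): "All AEs and SAEs must be recorded from the time a participant consents to join the study until hospital discharge". Record review then extends to 90 days.
- AEs are actively sought before the bolus (Protocol 7.1.9): "Adverse events/ adverse reactions will be assessed at baseline, 2hr, 2.5hr 10hr, 20hr and 22hr". The schedule in Protocol 7.2 defines baseline as before PP100-01.
- The bolus follows the loading infusion (Protocol 7.1.7): "Immediately prior to PP100-01 a study specific blood sample will be collected (time 2hr". Protocol 7.1.11 adds: "PP100-01 treatment should be +/- 10mins of timepoint".
- Consent may come after NAC has begun. NAC is started on suspicion of overdose, and in the synopsis (Baseline Assessments) patients "will be asked if they will participate in the study once their blood results are available".

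**The concern.** The primary objective is the safety of PP100-01 added to NAC. An event that starts before the bolus says nothing about PP100-01, yet it settles that patient's any-AE status. A patient who vomits during loading is already counted, so further vomiting after the bolus changes nothing in the contrast.

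The overlap is plausible here. Protocol 3.2 says that reactions under the standard NAC regimen generally occur during or soon after loading. Protocol 2.3 names severe vomiting and an immediate fall in blood pressure as potential risks of the study drug. A background NAC effect and a watched-for PP100-01 effect can therefore be the same symptom on either side of the 2 h mark. At stake is how clearly the primary table shows what followed the drug.

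**Working it through.** **Inputs.** From the documents: 6 patients per dose group, 2 NAC-alone patients per cohort (6 pooled), bolus at 2 h ± 10 min after NAC start. The plan states no AE rate, power or alpha for this comparison, so there is no figure of its own to reproduce. Assumed for illustration: q = 5%, 15% or 30%, and post-bolus AE rates of 50% (PP100-01 + NAC) v 20% (NAC alone).

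The documents do not bound q well. Protocol 2.2.2 gives about 15% anaphylactoid reactions, 60.4% vomiting and 70.4% nausea. Those are whole-course rates on the older regimen; Protocol 3.2 says the 12 h regimen lowers vomiting and anaphylactoid reactions. If consent follows NAC start, q is smaller still.

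**Step 1: general form.** Let p be an arm's post-bolus AE rate and p₁ that rate among its patients with a pre-bolus AE. Then P(any AE) = q + p − q·p₁. With q equal in both arms by randomisation:

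any-AE difference = (p_T − p_C) − q × d1, where d1 = p₁_T − p₁_C.

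**Step 2: independence.** Then d1 = p_T − p_C, and the difference shrinks by the factor (1 − q).

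| q | Any-AE rates | Difference (points) | Patients lost in six (6 × 0.30 × q) | P(excess ≥ 2 patients), 6 v 6 | Two-sided Fisher power, 6 v 6 |
|---|---|---|---|---|---|
| 0 | 50% v 20% | 30 | 0 | 58.5% | 3.5% |
| 5% | 52.5% v 24% | 28.5 | 0.09 | 56.2% | 3.4% |
| 15% | 57.5% v 32% | 25.5 | 0.27 | 51.7% | 3.0% |
| 30% | 65% v 44% | 21 | 0.54 | 45.2% | 2.1% |

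The last two columns come from exact binomial enumeration. Fisher's test stands in because the SAP does not name its exact interval method.

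**Step 3: without independence.** Take q = 30% and an overall difference of +30. If patients with a pre-bolus AE have post-bolus rates of 80% v 60%, then d1 = 20 and the result is 30 − 0.30 × 20 = +24, not +21. If d1 = 0, nothing is lost.

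**Step 4: a common anchor at 1 h 50 min.** Assume independence, the bolus at 2 h, and pre-bolus events spread evenly over 0–2 h. The share left between anchor and bolus is q × 10/120 = 0.42%, 1.25% or 2.5%. The +30 then shows as +29.87, +29.62 or +29.25, and P(excess ≥ 2) is 58.3%, 57.9% or 57.3%. With the bolus at 2 h 10 min (q × 20/120) the differences are +29.75, +29.25 and +28.5. A bolus delayed further leaves more.

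**Step 5: why the anchor must be common.** Protocol 9.3 allows the infusion to be interrupted for a reaction, which can delay the bolus. Suppose the treated arm were counted from the actual bolus and NAC alone from nominal 2 h. Loading events after 2 h in delayed patients would then count only in NAC alone. With no drug effect, the bias is −d × r × (1 − a): d is the share with a delayed bolus, r the chance of an AE between 2 h and the delayed bolus, and a the later AE rate. With assumed d = 15%, r = 30%, a = 30%: −0.15 × 0.30 × 0.70 = −3.15 points. One anchor timed from NAC start removes this.

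**The case against.** **No decision turns on it.** The assumed loss is at most about half a patient in six, Fisher power is negligible either way, SAP 4.4 allows a retreat to descriptive summaries, and escalation runs through the safety committee. All true, and it limits the severity. But the fallback tables have no post-bolus start either.

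**Existing coverage.** SAP 4.9 lists every AE with start date and time and relationship to PP100-01. Protocol 10.4.2 makes timing a causality criterion, so an event that began before the bolus should be judged unrelated. Vital signs (change from baseline) and ECG (against baseline) are analysed at 2.5 h. With 24 patients these are real checks, and it would be wrong to infer that the plan cannot show what followed the bolus. None of them gives a like-for-like AE comparison with NAC alone.

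**The all-events comparison is legitimate.** NAC is itself a study medication, and Protocol 1.1 wants adverse effects of the combined regimen. This stands, and is why that comparison should stay.

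**Stronger readings.** A reader might infer that the planned contrast is biased for or against PP100-01. It is not: randomisation balances pre-bolus events in expectation. A reader might also treat (1 − q) as the certain loss, or put the 60–70% nausea and vomiting rates in for q. The first needs independence; the second uses whole-course rates from another regimen. Nor is the SAE contrast equally affected, since few SAEs are likely between consent and bolus.

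**Conclusion.** The omission is clear from the text: the AE/SAE comparison has no onset limit, the only windowed rows start at NAC, and no AE table starts at the bolus. The consequence is possible attenuation of the any-AE contrast as a reading of PP100-01, by q × d1. Its size is uncertain. It is 1.5 to 9 points on an assumed +30 if q is 5% to 30% and events are independent, less if d1 is smaller, and close to nil if consent usually follows most of the loading infusion. The calculation assumes equal pre-bolus risk and recording in both arms.

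Severity is minor. The gain is a clearer, pre-specified reading of which events followed the bolus, not a test.

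**What to change.** In SAP 4.4, leave the all-events comparison and the analysis populations unchanged and add:

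1. One supplementary any-AE comparison, with the same differences and exact 95% intervals, for events with onset from a common anchor up to 7 days after consent. Time the anchor identically in both arms from the start of the first NAC infusion, for example 1 h 50 min, the earliest bolus time the protocol window allows.
2. Counts only for pre-anchor AEs, AEs after day 7, and SAEs by the same windows.
3. One rule, applied to both arms, for a missing or unclear onset time, for example counting the event as post-anchor. This is needed because Protocol 10.4 asks only for the date of onset, although SAP 4.9 lists time as well.
4. A flag for pre-anchor events recorded as worsening after the anchor.

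The cost is low. Onset times are already listed (SAP 4.9), and NAC start time is already needed for SAP 4.3. The addition is six descriptive intervals (three within cohort, three against pooled NAC alone) and a few count rows.

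The downsides are reliance on recorded onset times near the anchor, and loading-infusion events between the anchor and a late or delayed bolus. Those still count, but equally in both arms.

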- 1. Start "loading" dose: 100 mg/kg NAC diluted in 200 ml diluent* i.v. over 2 hours
- 2. PP100-01 bolus infusion over 5 minutes
- 3. Second dose: 200 mg/kg NAC diluted in 1000 ml diluent* i.v. over 10 hours

* diluent is 5% Dextrose or 0.9% Sodium Chloride.

Investigational Medicinal Product: PP100-01 given as one dose after the initial "loading" dose with NAC.

- Group A: PP100-01 (2 µmol/kg calmangafodipir) after the "loading" dose of NAC
- Group B: PP100-01 (5 µmol/kg calmangafodipir) after the "loading" dose of NAC
- Group C: PP100-01 (10 μmol/kg calmangafodipir) after the "loading" dose of NAC

In each dosing cohort there will be 8 patients randomly allocated to PP100-01 and NAC (N=6) or NAC alone (N=2).

Patient population:

Any patient requiring treatment with NAC (confirmed by blood tests) for acute paracetamol/ acetaminophen overdose arriving to the hospital < 24hr after paracetamol/acetaminophen overdose (POD).

Study Purpose:

The study with PP100-01 in combination with NAC is designed to determine safety and tolerability of PP100-01 when co-administered with NAC as compared to the 12-hr NAC treatment regime for patients that come to the hospital after an overdose of paracetamol/acetaminophen.

As a secondary objective possible efficacy will be explored by using experimental biomarkers in serum/plasma, such as CK18 and microRNA MiR122, GLDH, mitochondrial DNA and others that might give efficacy signals for PP100-01. The diagnosis of paracetamol/acetaminophen overdose will be made by ALT and paracetamol/acetaminophen measurements.

This study includes several comparisons;

- Safety and tolerability of PP100-01 + NAC vs NAC alone
- Assess hepatotoxicity in patients after POD as assessed using ALT, INR and experimental biomarkers of liver damage

Primary Objective:

Investigate the safety and tolerability of PP100-01 add-on treatment to the 12hr NAC treatment regime in patients treated for paracetamol/acetaminophen overdose (POD) when NAC treatment is initiated before 24hours post POD.

Secondary Objective:

Determine if there is evidence of PP100-01 having efficacy with regard to treatment of paracetamol-induced liver injury by measurement of conventional clinical biomarkers and novel experimental biomarkers.

Study Design:

The study will be an open label, randomised, exploratory, rising dose design, NAC controlled, phase 1 safety and tolerability study in patients treated with NAC for paracetamol/acetaminophen overdose.

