6.6 Treatment Allocation

6.6.1 Treatment Allocation Procedure

Eligible patients will be allocated to treatment according to a rising dose design. Allocation of patients to each dose will need to be completed before allocation can start for the next dose. In each dosing cohort there will be 8 patients. 6 will receive PP100-01 and NAC and 2 NAC alone. There will be a randomisation process at entry to the study that will determine treatment allocation within dosing cohort.

- Group A: PP100-01 (2 µmol/kg calmangafodipir) after the "loading" dose of NAC
- Group B: PP100-01 (5 µmol/kg calmangafodipir) after the "loading" dose of NAC
- Group C: PP100-01 (10 µmol/kg calmangafodipir) after the "loading" dose of NAC

Once a patient is allocated a treatment number he/she will remain in the study and have all outcomes recorded, unless he/she specifically withdraws consent to have data stored.

All medical and nursing staff caring for the patient will know (open label) treatment allocation. PP100-01, specially prepared and packaged for clinical study purposes, will be prepared and labelled to patient allocation number. Stores of packs will be held within the hospital pharmacy and sufficient packs supplied to the Emergency Department as required.

Doses of NAC and PP100-01 are based on the patient's weight and therefore infusions need to be prepared individually for each patient. NAC will be prepared by the clinical team or a delegated member of the research team and PP100-01 by a delegated member of the research team according to the 'Site Instructions for handling the IMP'.

A period of 24 hours will be left between recruitment of the first participant allocated to PP100-01+NAC treatment in each dosing cohort and recruitment of the next participant to allow adequate time for early adverse events to be identified.

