6.6.2 Randomisation

The allocation sequence for each dosing cohort will be created using computer-generated random numbers, using blocking to ensure the required 6:2 ratio of NAC+PP100-01:NAC alone. The randomisation list will be held centrally at the Edinburgh Clinical Trials Unit (ECTU) in order to conceal treatment allocations until these are implemented via the ECTU secure web-based randomisation system.

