12.4 Proposed Statistical Analysis

A CONSORT diagram depicting the flow of participants through the study will be reported. Descriptive statistics will be used to report baseline characteristics by treatment group and overall: continuous variables will be summarised by the mean, standard deviation, median minimum and maximum; categorical variables will be summarised using the number and percentage in each category. Log transformation will be used where appropriate.

We will keep missing data to an absolute minimum, but where there is missing data those records will be removed from the analysis; if missing data rates are substantial the effect of this will be investigated using sensitivity analyses.

Binary outcomes (including the primary outcome) will be reported by treatment group and overall using the proportion and exact 95% confidence interval. Binary outcomes will be compared within dosing cohort between the PP100-01+NAC and the NAC alone patients using a difference in proportions and its exact 95% confidence interval. Binary outcomes will be compared between each of PP100-01 dosing groups A, B and C and the combined NAC alone group in the same way.

Continuous outcomes will be reported by treatment group and overall using the mean and 95% confidence interval. Continuous outcomes will be compared within dosing cohort between the PP100-01+NAC and the NAC alone patients using the difference in means and its 95% confidence interval. Continuous outcomes will be compared between each of PP100-01 dose groups A, B and C and the combined NAC alone group in the same way. The continuous outcome analyses listed above will be repeated using the change from baseline in each continuous outcome.

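### SAP 4.4 never combines its three randomised within-cohort safety contrasts into one comparison of PP100-01+NAC with NAC alone, and it lets the planned intervals be dropped after events are seen, with no threshold

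*SAP*

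**What the plan says.** - **Comparison named.** The protocol synopsis lists among the study's comparisons "Safety and tolerability of PP100-01 + NAC vs NAC alone", and its design paragraph adds: "The study will primarily evaluate safety and tolerability for treatment with PP100-01 in combination with NAC as compared to NAC alone". SAP 3.3 has the safety population analysed by treatment received, in those two groups.
- **Allocation.** Three cohorts of 8 are filled in sequence: "Allocation of patients to each dose will need to be completed before allocation can start for the next dose" (protocol 6.6.1). Within each, the list is generated "using blocking to ensure the required 6:2 ratio of NAC+PP100-01:NAC alone" (protocol 6.6.2).
- **Planned contrasts.** SAP 4.4: "AE and SAE proportions will be compared within each dosing cohort between the PP100-01+NAC and the NAC alone patients using a difference in proportions", with an exact 95% confidence interval. Each dose is also set against all NAC alone patients. Protocol 12.4 plans the same two sets; the second reads "Binary outcomes will be compared between each of PP100-01 dosing groups A, B and C and the combined NAC alone group". The overall column pools both arms, so it is not a contrast. The SAP's tabulation by treatment received is made inside each cohort only.
- **Fallback.** SAP 4.4: "If the limited sample size or a small number of observed events leads to a lack of interpretability" of the formal intervals, then "the analysis of the primary outcome will be restricted to descriptive summaries only". No threshold, decision-maker or time is given. Protocol 12.4 contains no such provision.

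**The concern.** The safety question is framed as drug plus NAC against NAC alone, yet no planned interval answers it with all the randomised information together. The 6 v 2 contrasts have the right controls but only two of them each. The 6 v 6 contrasts have more controls, but four of the six were recruited in other cohorts, at other times.

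When few SAEs occur, the main formal statement a small safety study can make is an upper limit on the excess risk. That is also a situation in which SAP 4.4 allows the intervals to be left out. Both triggers can be foreseen: the size is fixed at 24, and protocol 12.3 says that no adverse events are expected. The decision would be taken after events are seen, in an open-label trial.

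**Working it through.** **Inputs.** 3 cohorts × (6 + 2) = 24, which matches the protocol's total and gives 18 on PP100-01+NAC and 6 on NAC alone. Intervals are two-sided 95% (SAP 3.2). Protocol 12.3 gives no power, effect size or event rate, so there is no precision figure to reproduce.

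**The pooled difference keeps randomised, concurrent control.** With x events of 6 and y of 2 in each cohort, the equally weighted mean of the three within-cohort differences is

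(1/3) Σ(x/6 − y/2) = Σx/18 − Σy/6,

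which is the crude 18 v 6 difference. This holds while every cohort is 6:2.

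**Exact intervals.** The upper limit is the largest δ for which the probability of a result at least as low as the one observed, maximised over the background risk, exceeds 2.5%. The ordering of results must be chosen. Raw ordering uses p₁ − p₂. Score ordering uses (p₁ − p₂ − δ) divided by its standard error at the restricted maximum-likelihood estimate. The SAP says only that the interval is exact, so both are shown, in percentage points:

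| Result | Ordering | 6 v 2 | 6 v 6 | 18 v 6 |
|---|---|---|---|---|
| No events, upper limit | score | +46 | +46 | +21 |
| No events, upper limit | raw | +84 | +58 | +47 |
| One event on PP100-01, none on NAC alone, upper limit | score | +64 | +64 | +29 |
| One event on PP100-01, none on NAC alone, upper limit | raw | +84 | +70 | +51 |
| 50% v 50% | score | ±71 | ±58 | ±44 |
| 50% v 50% | raw | ±84 | ±58 | ±47 |

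Limits are on a 0.2-point grid; a one-point grid gives about 57 and 46 for the raw 58 and 47. Raw ordering treats all tables with the same observed difference alike, so its no-event and 50% v 50% rows agree.

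A hand check explains the first row. With 0 of 6 treated patients affected and no background risk, (1 − δ)⁶ = 0.025 gives δ = 1 − 0.025^(1/6) = 0.459. Going from 2 to 6 controls therefore does not move the +46; only more treated patients do.

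**Chance that the interval excludes zero** (score ordering, assumed rates not in the documents, same effect at every dose), 6 v 6 then 18 v 6:
- 80% v 30%: 39%, 59%
- 80% v 50%: 14%, 26%
- 30% v 10%: 4%, 3%, so no gain on this measure for rarer events

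**Non-concurrent controls.** The documents give no drift figure. As an illustration only, background risks of 45/50/55% in cohorts A, B and C give a combined-control mean of 50%. The 6 v 6 contrasts for A and C would then be off by 45 − 50 = −5 and 55 − 50 = +5 points. The 18 v 6 difference would not be shifted. Its ordinary exact score interval keeps 96.0% coverage at zero effect when the cohort risks are 40/50/60%.

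**Fallback trigger.** There are 7 × 3 = 21 possible 6 v 2 tables. In 19 of them the exact interval is wider than 100 points, under either ordering. The 100-point mark is chosen here for illustration, but it shows that limited size could be argued for almost any result.

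**The case against.** - **All 24 patients are already used in randomised, concurrent comparisons.** True. A reader might infer that 18 v 6 is the only such contrast, or that the named comparison is never made. The documents do not support either: the three 6 v 2 contrasts are randomised and concurrent and between them use everyone. What is missing is their combination and its interval.
- **The SAP follows the protocol.** On the contrasts it does. The synopsis does not say that doses are to be pooled. On the fallback clause the SAP goes beyond the protocol.
- **Pooling hides dose effects.** This stands as a limit. If an assumed 50-point effect (80% v 30%) exists at the top dose only, the pooled difference is 50/3 ≈ 17 points. Its chance of excluding zero is 7%, against 39% for that dose's own 6 v 6 contrast.
- **The benefit depends on the ordering.** Correct. A fall from +46 to +21 holds only under score ordering. Under raw ordering, the 18 v 6 limit of +47 is about what the planned 6 v 6 already gives under score ordering. Pooling tightens the limit either way, and naming the ordering helps the planned contrasts at no cost.
- **No events at all is unrealistic.** For all AEs, yes: protocol 2.2.2 reports nausea in 70.4% and vomiting in 60.4% of a cohort given NAC. The no-event case is realistic only for SAEs.
- **The fallback loses little.** Counts, percentages, tables by system organ class and patient listings would still appear. A reader might infer that safety data could be withheld; the SAP does not allow that. Only the formal intervals could go.

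**Conclusion.** The point holds as a cheap improvement. The plan omits a combined estimate of the safety comparison that the protocol names, leaves the exact method unspecified, and makes its primary intervals optional after the data are seen, without a rule.

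With no SAEs, the combined contrast lowers the upper limit on excess risk from +46 to about +21 points under score ordering. Under raw ordering it goes from +84 (6 v 2) or +58 (6 v 6) to about +47. These figures assume that 6:2 is kept in every cohort. The interval remains wide, and the study is exploratory with no stated power.

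Two stronger readings are not supported. First, the 6 v 6 contrasts are not shown to be biased: four of six controls are non-concurrent, but nothing in the documents quantifies drift. Second, the case does not extend to pooled analyses of hepatotoxicity or hospital stay, because protocol section 4 defines those comparisons against the individual PP100-01 arms.

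**What to change.** For AEs and SAEs in SAP 4.4 only:

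1. Add, as a supplement to the dose-specific contrasts, one difference in proportions for all PP100-01+NAC (18) against all NAC alone (6), stratified by dosing cohort, with an exact 95% confidence interval. Name score ordering for this and every other exact interval for a difference. If replacement (protocol 6.7) or analysis by treatment received (SAP 3.3) breaks 6:2 in any cohort, use a cohort-stratified exact interval.
2. Keep the 6 v 2 and 6 v 6 intervals, and label the 6 v 6 ones as partly non-concurrent, with 4 of 6 controls from other cohorts.
3. Replace the descriptive-only sentence with a commitment to report all planned differences and their exact 95% intervals, and the cohort-stratified difference, whatever their width.

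The cost is SAP wording and one more use of a routine that the planned contrasts already need. No new data are required. A stratified exact routine is needed only if 6:2 is broken. The downside is that the pooled estimate averages over doses from 2 to 10 µmol/kg, so it should be presented beside the dose-specific results and never in their place.
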